5.16.2 Analysis of secondary endpoints

Decisional Conflict

Decisional Conflict Scale (DCS) will be calculated according to published methods. A mean of the 16-item scale (rated on a 5-point scale) will be taken and multiplied by 25 to produce summary scores ranging from 0-100 points.^{71,74} Descriptively, summary scores will be presented descriptively (mean and SD across participants in each arm by study). We will compare DCS scores across in the SDM intervention condition to the SOC counselling control condition in an exploratory manner. We hypothesize that the intervention will be superior to the control, with intervention participants reporting at least an 8-point lower decisional conflict score on average than control participants. An intent-to-treat approach will be used to evaluate the effect of treatment on decisional conflict. We will first compare group means of decisional conflict scores by study arm and then examine the intervention's effect on this outcome using a two-sample Welch's t-test. If demographic variables related to decisional conflict differ substantively by study arm, we will instead use augmented inverse probability weights (AIPW) to perform doubly robust estimation of the average intervention effect to compare intervention vs. control (e.g., using the CAUSALTRT procedure in SAS software). Missing (unevaluable) data are anticipated to be uncommon ($\leq 10\%$). Multiple imputation methods will be applied to address missing data if appropriate.

Exploratory analyses will also be conducted with a dichotomous coding of DCS score according to published thresholds. A "low" DCS score will be identified using a cut-off of 25 out of 100, which has been linked to reduced decisional regret and enhanced choice retention. DCS scores will be computed based on women's responses to statements, where higher scores indicate greater decisional conflict, while lower scores indicate diminished conflict and heightened certainty in decision-making.

5.16.3 Quantitative analysis of exploratory endpoints

We will examine the intervention effect on retention and PrEP adherence in an exploratory fashion. In order to evaluate effectiveness, analyses will be conducted using an intention-to-treat approach, with women analysed according to the arm they were randomly assigned.

Given the pilot nature of these studies, emphasis will be put on estimation and precision of measured effects, rather than null hypothesis testing. An alpha=0.05 will be used throughout to compute 95% confidence intervals (CIs), with no adjustment for multiplicity. In the case of small cell counts (<5), 95% CI coverage properties of large-sample methods will be evaluated using exact statistical methods (e.g., exact CI for a risk difference) in sensitivity analyses. Given potential for precision loss with exact CI methods and the pilot nature of these studies, we will use large-sample methods (e.g., Wald CIs) when the nominal CI coverage level is tenable.

Missing (unevaluable) data are anticipated to be uncommon ($\leq 10\%$). The primary analyses are based on a composite endpoint of being retained in care with functional PrEP use, and thus complete case analyses will be conducted. Women who are not retained in care will be counted in the denominator for the primary analysis. Sensitivity analyses will exclude women who were not retained in care.

PrEP uptake

Uptake of oral PrEP will be described as the proportion of participants with record of receipt of an oral PrEP prescription.

Retention + Functional Adherence

Our clinical exploratory endpoint to be measured among participants taking up PrEP is retention in care with functional adherence to PrEP at two months. We will assess adherence to oral PrEP among participants taking it up through Tenofovir diphosphate (TFVdp) concentrations in participant dried blood spot (DBS) samples. TFVdp will be measured using

established liquid-chromatography tandem mass spectrometry methods⁷⁵ Using published thresholds⁷⁶, TDFdp concentrations will be categorized as in Table 10 below. Emtricitabine triphosphate (FTCtp) concentrations will also be quantified and may be interpreted in an exploratory manner (e.g., in the event that TDFdp is below the level of quantification). Participants will be considered for this composite outcome if they have any record of oral PrEP initiation following study assisted referral. Participants retained at two months meeting the relevant definition of functional adherence (below) will be categorized as retained with functional adherence.

Table 10. Adherence interpretation of TDFdp concentration levels

Interpretation	DBS TDFdp fmol/punch	
	Pregnant participants	Postpartum participants*
~7 doses/week	≥650	≥1050
2-6 doses/week	200-649	300-1049
<2 doses/week	<200	<300

*participants will be enrolled during pregnancy but may deliver prior to the month 2 visit when this outcome is assessed

Treatment effect on PrEP adherence among participants adopting PrEP will be explored as sample size and rates of adoption permit. We will compare the proportion of the sample retained in care with functional PrEP adherence at 2-month follow-up between the two randomization arms using a linear-binomial model. Women who are not retained for 2-month follow-up will be counted as failures and will contribute to the analysis denominator. From the linear-binomial model, the site-adjusted risk difference of being retained and in care with functional PrEP for the intervention arm versus the control arm will be calculated, along with a corresponding 95% CI.

In addition to the primary analysis, assessing functional PrEP adherence as binary outcome, secondary analyses will compare the adherence categories between the study arms using a Wilcoxon rank-sum test. This analysis will be restricted to women with an evaluable adherence score.

Intervention Fidelity

To assess intervention fidelity, we will quantify intervention fidelity in a series of items rated by a study team member on a 5-point scale. A random subset (~20%) of these sessions will be audited by a study team member using a fidelity assessment tool that includes objective and subjective measures. These assessments will help to characterize the quality of implementation over the course of study participation. Fidelity to the intervention will be assessed through study staff audits of counseling sessions on including quality of counseling delivered (adherence to intended components and quality of counseling delivered), for of each section of the counseling and overall, with elements rated on a 5-point scale (0 “no effort” to 4 “exemplary effort”). Ratings for each section of the scoring instrument tool will be averaged and summarized descriptively (including mean scores and standard deviations) to report fidelity to the intervention.

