5.9.3 Assessment of exploratory outcomes

PrEP uptake

We will assess PrEP uptake (i.e., receipt of oral PrEP prescription) among participants choosing PrEP during the intervention session. This will be assessed through clinic or pharmacy records.

Retention with functional adherence

Our clinical exploratory endpoint to be measured among participants taking up PrEP is retention in care with functional adherence to PrEP at two months. Retention will be assessed through study records. For participants taking up oral PrEP, functional adherence will be measured categorically according to Tenofovir diphosphate (TFVdp) quantified in dried blood spot (DBS) samples at the 2-month visit.

Intervention Fidelity

Intervention sessions will be digitally audio recorded with participant consent. A random subset of sessions will be reviewed by a study team member using a structured tool to assess intervention fidelity. Study staff will use recordings to evaluate the quality of counseling delivered (adherence to intended components and quality of counseling delivered) using a structured tool. Raters will score each section of the counseling and overall, with elements rated on a 5-point scale (0 "no effort" to 4 "exemplary effort").

Qualitative assessment of intervention & study procedure perceptions

Qualitative in-depth interviews (IDIs) with study participants will be conducted at the visits designated above to explore women's satisfaction with study counseling, session quality, and feeling about their decision. Follow-up interviews will evaluate women's experience using their selected HIV prevention method and the perceive impact of the study counseling on their current use of the selected product. Additional feedback on the intervention and study procedures will be gathered.

Additional IDIs will be conducted with male partners and study staff to gather insights into their experiences with the intervention, different procedures, perceptions of integrating Shared Decision-Making (SDM) into routine care, and suggestions for procedural improvements.

IDIs will be conducted by a locally recruited and trained research assistant fluent in Chichewa and English using semi-structured interview guides. Interviews will be digitally audio-recorded, transcribed, and translated to English for analysis.

Table 5. Schedule of Evaluations

	Screening	Enrollment	Month 1	Month 2	Month 3
Eligibility assessment					
Pregnancy status	X				
HIV status	X				

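### The exploratory adherence comparison is called intention-to-treat but admits only women who started PrEP; add an all-randomised risk difference and uptake by arm, and label the initiators-only result as non-randomised

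*Protocol*

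**What the plan says.** Protocol 5.16.3 opens with the principle: "In order to evaluate effectiveness, analyses will be conducted using an intention-to-treat approach". It explains this as analysing women by assigned arm.

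The population is then narrowed in three places:

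- Section 5.9.3 describes retention with functional adherence as an "exploratory endpoint to be measured among participants taking up PrEP", and 5.16.3 repeats this.
- Before Table 10, 5.16.3 sets the entry criterion: "Participants will be considered for this composite outcome if they have any record of oral PrEP initiation following study assisted referral".
- After Table 10 it says: "Treatment effect on PrEP adherence among participants adopting PrEP will be explored as sample size and rates of adoption permit".

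The next sentence of 5.16.3 is looser. The plan is to "compare the proportion of the sample retained in care with functional PrEP adherence at 2-month follow-up between the two randomization arms", using a linear-binomial model that gives a risk difference and 95% CI. Women not retained at month 2 count as failures. Nothing is said about randomised women who never start. A Wilcoxon comparison of adherence categories is limited to women with an evaluable result.

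On missing data, 5.16.3 refers to the composite endpoint, "and thus complete case analyses will be conducted", and also keeps non-retained women in the denominator.

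Uptake has two denominators. Section 5.9.3 says: "We will assess PrEP uptake (i.e., receipt of oral PrEP prescription) among participants choosing PrEP during the intervention session". Section 5.16.3 says: "Uptake of oral PrEP will be described as the proportion of participants with record of receipt of an oral PrEP prescription". No between-arm estimate of uptake is specified.

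**The concern.** Whether a woman starts PrEP is settled after randomisation, and the counselling is directed at that decision. The problem statement in Protocol section 2 gives shared decision making the task of identifying appropriate users, and section 5.2 lets a woman defer or decline. The women who start in the MyChoice arm may therefore differ, in number or in kind, from those who start under standard of care. Comparing the arms among starters then mixes any effect on adherence with an effect on who starts.

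The Abstract says the pilot will inform an efficacy trial in which PrEP adherence is one of the outcomes. An initiators-only difference reported under an intention-to-treat heading could be carried into that trial's assumptions as an effect on adherence. Better fit among starters may be exactly what the counselling intends, but it would then be partly a selection result and should be labelled as one. Uptake by arm would help a reader judge this, and the plan does not ask for it as a comparison.

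**Working it through.** **The plan's own figures.** The documents give no precision, uptake rate or adherence rate for this endpoint, so there is no stated figure to reproduce. The nearest are the ± values in Tables 8 and 9. They follow from 1.96 × √(p(1−p)/n): with p = 0.8, n = 50 gives 0.111 and n = 45 gives 0.117, as printed. The same large-sample approach is used below.

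**Inputs.** From the documents: 100 women randomised 1:1 (5.1 and 5.7.2), so 50 per arm, and 95% CIs (5.16.3). Assumed: all counts of starters and of adherent women. Adherent women are fixed at 14 per arm, so the all-randomised difference is 0 by construction and the effect of the denominator can be seen alone.

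**Formula.** d = p₁ − p₂, with CI d ± 1.96 × √(p₁(1−p₁)/n₁ + p₂(1−p₂)/n₂), MyChoice minus standard of care, in percentage points.

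**All randomised.** 14/50 v 14/50: d = 0, half-width 1.96 × √(2 × 0.28 × 0.72/50) = 0.176, so 0 (-17.6 to +17.6) in every row below.

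| Starters, MyChoice v SOC | Adherent among starters, % | Initiators-only difference (95% CI) | Uptake difference (95% CI) |
|---|---|---|---|
| 30 v 30 | 46.7 v 46.7 | 0 (-25.2 to +25.2) | 0 (-19.2 to +19.2) |
| 28 v 32 | 50.0 v 43.8 | +6.3 (-19.0 to +31.5) | -8.0 (-27.1 to +11.1) |
| 26 v 34 | 53.8 v 41.2 | +12.7 (-12.6 to +38.0) | -16.0 (-34.9 to +2.9) |
| 23 v 35 | 60.9 v 40.0 | +20.9 (-4.8 to +46.6) | -24.0 (-42.8 to -5.2) |

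Worked row, 26 v 34: 14/26 − 14/34 = 0.538 − 0.412 = 0.127; half-width 1.96 × √(0.538 × 0.462/26 + 0.412 × 0.588/34) = 0.253. Swapping the arms reverses every sign.

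**The two measures can point in opposite directions.** Assume 40 v 25 starters and 20 v 15 adherent women. Among starters, 20/40 − 15/25 = -10.0 (-34.7 to +14.7). Among all randomised, 20/50 − 15/50 = +10.0 (-8.6 to +28.6).

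**What uptake can show.** At the mid-range uptake in the table, gaps of 8 and 16 points have intervals that include 0, so an unremarkable uptake comparison would not rule out selection. This depends on the level of uptake. With 37/50 v 45/50, the 16-point gap has half-width 1.96 × √(0.74 × 0.26/50 + 0.90 × 0.10/50) = 0.147, giving 1.3 to 30.7, which excludes 0.

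**The case against.** **The label is defined and met.** Section 5.16.3 explains intention-to-treat as analysis by assigned arm, and an initiators-only comparison satisfies those words. The section also says openly that the effect is among adopters and is exploratory. This stands as far as it goes. But the stated purpose is to evaluate effectiveness, and that is not served when randomised women drop out of the analysis because of an event after randomisation.

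**The text may already mean all randomised women.** The wording about the proportion of the sample allows that reading. It follows directly on a sentence about adopters and does not override the explicit initiation criterion. If all randomised women were intended, the two statements conflict and the denominator still has to be stated.

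**The illustration is built to show a contrast.** This is correct. Fixing 14 adherent women per arm forces the all-randomised difference to 0. The two measures also answer different questions (coverage, and adherence among starters), so a gap between them does not by itself demonstrate bias. Every adherence interval shown includes 0.

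**Declining PrEP is a legitimate outcome of the counselling.** Also correct. An all-randomised measure counts a woman who reasonably chooses condoms as a non-success. That is a reason to label it carefully and keep the initiators-only figure beside it, since section 3.3 is interested in adherent use.

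**Describing uptake fits Aim 3.** It does, and asking for a between-arm estimate is partly preference. The mismatch between the two uptake denominators remains.

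**Conclusion.** The concern holds in a limited form. The denominator of the adherence comparison is stated inconsistently. Its explicit criteria restrict it to women who started PrEP, and a risk difference on that group should not be presented as a randomised effectiveness contrast. With the assumed counts, the initiators-only difference ranges from 0 at equal uptake to +20.9 points at a 24-point uptake gap, while the all-randomised difference stays at 0. The real size is unknown because the documents give no uptake or adherence rate.

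Three stronger readings are not supported:

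- A reader might infer that the planned comparison will be biased. It is at risk of bias in either direction if uptake or the type of starter differs by arm, and unbiased if neither does.
- A reader might infer that uptake gaps of 8 or 16 points can never be told from 0 with 50 per arm. That holds at the uptake assumed in the table, and the 37/50 v 45/50 case shows that it is not general.
- A reader might count the SAP's silence as a further fault. SAP sections 3 and 4.4 confine it to the primary and secondary outcomes, so this is a matter of scope.

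The consequence is low: the endpoint is exploratory, the plan stresses estimation, and no primary or secondary result depends on it. It is a cheap improvement worth considering, held with moderate confidence given the ambiguous wording.

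**What to change.** In Protocol 5.16.3, or in the detailed analysis plan that section 5.16 promises before outcome analysis:

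1. Report as the intention-to-treat contrast the risk difference with 95% CI among all randomised women, labelled functional PrEP coverage and not decision quality. Count women who never start, and women not retained at month 2, as non-successes. Keep retained starters without an evaluable dried blood spot in the denominator as non-successes, with a sensitivity analysis using another handling, such as imputation or best-case and worst-case bounds. Excluding them, the natural reading of the complete-case wording, would bring back a post-randomisation exclusion. State whether women who start later, or without the study referral, count as initiators.
2. Keep the initiators-only risk difference and the Wilcoxon comparison beside it, both labelled exploratory and non-randomised.
3. Report uptake by arm among all randomised women with a risk difference and 95% CI, and reconcile the denominators in 5.9.3 and 5.16.3.

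As a clarification only, state before blood-spot results are seen which Table 10 categories count as functional. The text points to a definition that the table does not mark; no view is taken here on which is right.

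**Cost.** Wording and a few extra tabulations. Section 5.8 already plans initiation records for women choosing PrEP in either arm, and month-2 blood spots for oral PrEP users. Women who never start need no sample. The one added task is to check initiation records for all randomised women through month 2. The uptake assessment in Table 5 is at month 1 only, so it would miss later starts, and it is not clear that it covers every woman.

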5.16.4 Qualitative analysis of IDIs (exploratory outcomes)

Thematic analysis will be used to analyse the qualitative data. The transcripts will be transcribed and translated into English. Analysis will consist of: 1) Reading for Content: We will read the data until content becomes intimately familiar. As data are reviewed emergent themes will be noted. 2) Coding: A list of codes will be created and documented in a codebook based on identified themes in addition to structural codes corresponding to initial interview questions. Two coders will independently code each transcript. To ensure inter-coder reliability, 10% of data will be double-coded; 3) Data reduction: We will review the data related to each code to identify principal sub-themes that reflect finer distinctions in the data. This entails taking an inventory of what is related to a given code, observing the variation or

richness of each theme, and noting differences between individuals or among subgroups; 4) Data display and comparison: Matrices that categorize and display data will be used to help facilitate comparisons across the sampling groups.

6. ETHICAL CONSIDERATIONS

6.1 Ethical approval

All study participants will be fully informed of the study procedures described above. Prior to study activation, for each participating site, ethical approval will be sought from the relevant institutional review boards / research ethics committees, national authorities, and other regulatory authorities.

6.2 Informed consent

All participants will be consented prior to participation and during the consent process they will be reminded that their participation is voluntary. Discussions with prospective participants and informed consent procedures will be conducted in private to protect patient confidentiality. We will obtain written informed consent from all participants. The study procedures, risks, and benefits will be discussed and we will answer all questions prior to obtaining consent. The consent forms will be translated into relevant local languages and back-translated into English to assure accurate translation. For illiterate participants, a literate impartial witness will be present during the entire consent process to ensure that all of the relevant information has been provided and the participant voluntarily gives consent. Eligible women who do not wish to participate in this study will continue to receive ANC care according to local clinical standards. We will obtain signed permission from the pregnant woman to collect locator information, including phone numbers, addresses, and directions. Permission for collection of locator information and contract tracing will be per usual practice at the clinic.

6.3 Data storage

The confidentiality of all study records will be safeguarded to the extent legally possible. To maintain participant confidentiality, all laboratory specimens, reports, study data and administrative forms will be identified by a coded number only. All databases will be secured with password-protected access systems, and computer entries will be identified by coded number only. Forms, lists, logbooks, appointment books, and any other listings or data forms that link participant ID numbers to other identifying information will be stored in a separate, locked fireproof safe cabinet in a locked local office. For the data collected through audio recordings, all audio files will be deleted from the recorders after data are transferred into a computer. Study-related computers, tablets, audio tapes, field notes, and other study materials will be kept in a locked cabinet in a locked local office. All data analysis will be performed using datasets which have only study ID numbers as unique identifiers.

6.4 Confidentiality

Measures will be taken to ensure safety of data and confidentiality of all our study participants. All participants will be assigned a unique study ID number. The interview guides will not capture names of the participants but only their ID number. No study participant will be identified in any report or publication about this study. However, for quality control and safety purposes, data that we collect may be reviewed by the sponsor of this study (i.e. United States National Institute of Health), the ethical and regulatory committees in Malawi and at the University of North Carolina at Chapel Hill. Clinical information with individual identifiers will not be released without the written permission of the participant. We expect these procedures to adequately protect participant confidentiality.

6.5 Potential risks to participants

No study drug will be administered thus all risks to participants relate to risks relevant to counseling and study assessment procedures. The risk to participants in this study is minimal. The main risk is possible discomfort to participants in answering question about themselves

and their decisions or actions related to PrEP. All participants will be asked to provide written informed consent before participation in the study. During the consent process, we will inform all participants that they may stop at any time and may ask the interviewer to skip any questions they do not feel comfortable answering.

Participation in clinical research includes the risks of loss of confidentiality and discomfort with the personal nature of questions, particularly when discussing HIV infection or sexual behaviors. At each step in the study, we will protect participant privacy and confidentiality to reduce these risks (e.g., consenting participants in a private setting, not including names on case report forms, etc.). Although investigators will make every effort to protect participant privacy and confidentiality, it is possible that participant involvement in the study could become known to others, and that social harms may result (i.e., as participants could become known as HIV-positive). Participants will be given a phone number they can call at any time if they need assistance or feel they are at risk of harm.

Venipuncture is sometimes associated with discomfort. Venipuncture may lead to discomfort, dizziness, bruising, swelling, and rarely, an infection at the venipuncture site.

